9.5.3 Safety Analysis Set (SAS)

The Safety Analysis Set will consist of all subjects who received at least 1 dose of CVnCoV and for whom any post-vaccination safety data are available.

10.0 Conventions and Derivations

All data obtained in this trial and documented in the eCRF will be listed and summarized with sample statistics or frequency tables as appropriate. In all tables, listings and figures (TLFs), the co-morbidities definitions - chronic kidney disease, chronic obstructive pulmonary disease (COPD), obesity, chronic cardiovascular disease, chronic HIV infection, type 2 diabetes mellitus and post-renal transplantation - will be reported in this order.

The statistical analyses will be reported using tables, listings, and figures (TLFs). Templates will be provided in a separate document (TFL shells).

10.1 Baseline and Change from Baseline

Unless otherwise stated, baseline is defined as the last non-missing measurement at Visit 1 (Day 1), prior to administration of the first dose of trial vaccine.

Change from baseline = observed value at post-baseline time point – observed value at baseline

10.2 Fold Change from Baseline

Unless otherwise noted, fold change from baseline is defined as the ratio:

Post-baseline value/baseline value

10.3 Trial Day

Throughout this trial, trial days are defined as follows:

- Day 1 is the day of first trial vaccination.
- For days after first trial vaccination, trial day will be calculated as

Trial Day=Date of day – date of first dose + 1

- For days before first trial vaccination, trial day will be calculated as

Trial Day=Date of day – date of first dose

10.4 Case Definitions of Co-morbidities

Subjects with the following selected co-morbidities are at increased risk of severe illness from COVID-19 and will be included in the trial. Life expectancy of at least 1 year as per the Investigators' assessment is required for inclusion of the subject into the trial.

- **Chronic kidney disease:** Kidney function will be ascertained from the serum creatinine measurement within the last 6 months, converted into estimated glomerular filtration rate (eGFR) using the Chronic Kidney Disease Epidemiology Collaboration (CKD-EPI) equation, with impaired kidney function defined as eGFR <60 mL/min/1.73m².
 - Mild chronic kidney disease is defined as an eGFR between 60-89 mL/min/1.73 m².
 - Moderate chronic kidney disease is defined as an eGFR between 31-59 mL/min/1.73 m² with stable therapy and good maintenance over at least 6 months [1].
- **Chronic obstructive pulmonary disease (COPD)** (including emphysema and chronic bronchitis).
 - Mild COPD with or without cough or sputum production is defined as forced expiratory volume in 1 second/forced vital capacity (FEV₁/FVC) <0.7 and FEV₁ ≥80% predicted.
 - Moderate COPD with or without cough or sputum production is defined as FEV₁/FVC <0.7 and FEV₁ ≥50%, but <80% predicted with stable treatment (GOLD Criteria for COPD severity).
- **Obesity** with body mass index >32 kg/m².
- **Chronic cardiovascular disease** (heart failure, structural heart disorder, coronary artery disease, cardiomyopathies, arterial hypertension), including the following:
 - Heart failures (according to New York Heart Association [NYHA] classification [2]):
 - Class I: No limitation of physical activity. Ordinary physical activity does not cause undue fatigue, palpitation, dyspnea (shortness of breath).
 - Class II: Slight limitation of physical activity. Comfortable at rest. Ordinary physical activity results in fatigue, palpitation, dyspnea (shortness of breath).

- A structural heart disorder
 - without symptoms
 - with symptoms.
- Coronary artery disease:
 - Mild with metabolic equivalent threshold (MET)¹ <3, stable with medication.
 - Moderate with MET >3 – 5.9, stable with medication.
- Cardiomyopathies of non-infective and metabolic origin:
 - Mild with MET <3, stable with medication.
 - Moderate with MET >3 – 5.9, stable with medication.
- Hypertension (National Institute for Health and Care Excellence [NICE] categorization [4]):
 - Stage 1 hypertension: Clinic blood pressure ranging from 140/90 mmHg to 159/99 mmHg and subsequent ambulatory blood pressure monitoring (ABPM) daytime average or home blood pressure monitoring (HBPM) average blood pressure ranging from 135/85 mmHg to 149/94 mmHg.
 - Stage 2 hypertension: Clinic blood pressure of 160/100 mmHg or higher but less than 180/120 mmHg and subsequent ABPM daytime average or HBPM average blood pressure of 150/95 mmHg or higher.
- **Chronic HIV infection with stable aviremia (<50 copies/mL) and CD4 count >350/mL** as documented by blood samples taken within 12 months before enrollment. Viral load <50 copies/mL over 12 months with transient changes of 50-350 copies/mL is allowed.
- **Type 2 diabetes mellitus**, controlled with medication [$\text{HbA1c} < 58 \text{ mmol/mol (7.45\%)}; [(\text{HbA1c} \text{ in \%} - 2.15) \times 10.929 = \text{HbA1c in mmol/mol}]$]
- **Subjects with a renal transplant** at least a year ago under stable conditions for at least 6 months with medications, categorized as low risk of rejection.

Following inclusion of 25 cases of mild to moderate conditions under chronic kidney disease, COPD, chronic cardiovascular disease and diabetes mellitus, more severe conditions can be included into the trial upon iSCR and DSMB Chair approval and subjected to the clinical Investigator's decision. Under cardiovascular disease, the following cases can be included:

- Heart failures (according to NYHA classification [2]) Class III: Marked limitation of physical activity. Comfortable at rest. Less than ordinary activity causes fatigue, palpitation, or dyspnea (shortness of breath).
- Coronary artery disease: Severe with MET >6, stable with medication.
- Cardiomyopathies of non-infective and metabolic origin: Severe with MET >6, stable with medication.

¹ MET is defined as the amount of oxygen consumed while sitting at rest and is equal to 3.5 mL O₂ per kg body weight/min and is roughly equivalent to the expenditure of 1 kcal per kilogram of body weight per hour; 1 MET is the rate of energy expenditure while at rest. A 4 MET activity expends 4 times the energy used by the body at rest. Light MET is <3, moderate is 3 to 5.9 and vigorous is ≥6.0. MET 1 can take care of him/herself and may not maintain themselves and gets constraints on exertion. MET 4 can climb a flight of stairs or walk up a hill and can participate in other strenuous activities; >2-3 METs is fit normal person with well controlled with medication [3].

- Hypertension (NICE categorization [4]): Stage 3 or severe hypertension: Clinic systolic blood pressure of 180 mmHg or higher or clinic diastolic blood pressure of 120 mmHg or higher.
- Under diabetes mellitus, cases of uncontrolled diabetes mellitus with recent HbA1c of >59 mmol/mol (7.45%) with medication can be included. For uncontrolled diabetes mellitus, HbA1c should be within <10% variation and the subject should not have any history of diabetic ketoacidosis or episode of severe symptomatic hypoglycemia within the past 3 months.

10.5 Missing Data

In general, no imputation of missing values will be done except for the following:

- For SARS-CoV-2 RBD of S protein antibodies, and viral neutralizing antibodies, concentration values marked as below the lower limit of quantification (LLOQ) will be set to 0.5*LLOQ for computation purposes.
- Imputation of (partially) missing AE start dates:
 - If start date year value is missing, the date uncertainty is too high to impute a rational date. Therefore, if year value is missing, the imputed AE start date is set to missing.
 - If start date year value is before the vaccination start date year value, then the AE started before the vaccination. Therefore:
 - If month is missing, the imputed start date is set to the mid-year point (i.e., 01JULYYYY).
 - If month is not missing, the imputed start date is set to the mid-month point (i.e., 15MONYYYY).
 - If start date year value is equal to the vaccination start date year value, the start date month needs to be compared against the vaccination start date month, to determine the imputation rule to apply. Therefore:
 - If month is missing, the imputed month and imputed day is the same as start of vaccination
 - If month is lower than vaccination start date month and start date day is missing, the imputed start date is set to the mid-month point (i.e. 15MONYYYY).
 - If month is equal to the vaccination start date month and start date day is missing, the start day will be set to the start day of vaccination.
 - If month is greater than the vaccination start date month and start date day is missing, the imputed start date is set to the beginning of the month (i.e., 01MONYYYY).
 - If start date year value is greater than the vaccination start date year value, the AE started after vaccination. Therefore:
 - If month is missing, the imputed start date is set to the year start point (i.e., 01JANYYYY).
 - If start date month is not missing and start date day is missing, the imputed start date is set to the beginning of the month (i.e., 01MONYYYY).
 - If after imputation of start and resolution date (see below) a start date is after the resolution date (for example if a missing day of a start date is set to 15 and the resolution date is before the 15th of the same month and year) then the start date will be set to the resolution date.
- Imputation of (partially) missing AE end dates:
 - If date of resolution is completely missing, and it is assumed that it resolved at the date of the end of the trial, the date of the end of the trial is used as the AE end date.
 - If year is present, it is assumed that it resolved on 31 December of that year (i.e., 31DECYYYY), or at the end of the trial if this is earlier and in the same year.

- If year and month are present, it is assumed that it resolved on the last day of that month, or at the end of the trial if this is earlier and in the same month/year.
- Imputation of missing AE start times:
 - If the (recorded or imputed) AE start date is equal to the vaccination start date, then the AE start time will be the time of vaccination start.
 - In all other cases, AE start time will be imputed as 00:00.

If not stated otherwise, the original or incomplete data will be presented in listings rather than the imputed one.

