10.7.1 Treatment Emergent Adverse Events (TEAEs)

A TEAE is any AE that first occurs or increases in severity or relationship to trial vaccine after the first dose of vaccine. AEs which change in severity or relationship to trial vaccine are assigned a new start date and captured as a new record in the CRF. Hence, an AE is defined as TEAEs if the start date/time is after the date/time of first vaccination. Imputed AE start date/time as defined in Section 10.5 will be considered when assessing if an AE is treatment emergent. If the AE start date is still missing after applying imputation rules (i.e. missing year), the AE will be considered treatment emergent.

All Solicited AEs are considered treatment emergent, even in the case that (partially) missing or conflicting date/time information is recorded or imputed.

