12.7.1.1 Analysis of Unsolicited AEs and Solicited AEs

An overall summary of unsolicited AEs will be prepared for AEs occurring within 28 days after each dose, within 28 days after any dose, and all reported AEs (including those reported at more than 28 days after any dose).

- Unsolicited AEs
- Related unsolicited AEs
- SAEs (includes solicited AEs)
- Related SAEs (includes solicited AEs)
- Grade 3 (severe) unsolicited AEs
- Grade 3 (severe) related unsolicited AEs
- Intercurrent medical conditions affecting immune response (includes solicited AEs)
- Medically attended AEs (includes solicited AEs)
- Related medically attended AEs (includes solicited AEs)
- AESIs (includes solicited AEs)
- Related AESIs (includes solicited AEs)
- Medically attended AEs (includes solicited AEs)
- Related medically attended AEs (includes solicited AEs)
- AESIs (includes solicited AEs)
- Related AESIs (includes solicited AEs)
- AEs leading to vaccine withdrawal
- AEs leading to withdrawal from trial

The overall summary will also be presented for overall and by sex (female/male)* and for any dose (dose 1 and dose 2) and include AEs for the duration of the trial.

The following summaries of unsolicited AEs by SOC and PT will further be provided, separately for AEs occurring within the first 28 days after each vaccination, within the 28 days after any vaccination, and all reported AEs (including those reported at more than 28 days after any dose) if not otherwise stated:

- Occurrence of unsolicited AEs
- Occurrence of related unsolicited AEs*
- Occurrence of SAEs (includes solicited AEs)*
- Occurrence of related SAEs (includes solicited AEs) *
- Occurrence of unsolicited AEs by maximum severity (mild / moderate / severe)*
- Occurrence of related unsolicited AEs by maximum severity (mild / moderate / severe) *
- Occurrence of SAEs by maximum severity (mild / moderate / severe) (includes solicited AEs)*

- Occurrence of related SAEs by maximum severity (mild / moderate / severe) (includes solicited AEs)*
- Occurrence of AESIs (includes solicited AEs)
- Occurrence of related AESIs (includes solicited AEs)*
- Occurrence of intercurrent medical conditions affecting immune response (includes solicited AEs)*
- Occurrence of medically attended AEs (includes solicited AEs)*
- Occurrence of related medically attended AEs (includes solicited AEs)*
- Occurrence of AEs leading to withdrawal from trial (includes solicited AEs)

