14.3.2 Adverse Events Data Tables
Table 14.3.2.1.1 Overall Summary of Adverse Events (Safety Analysis Set)
Table 14.3.2.2.1 Summary of Solicited Adverse Events and Maximum Grade Occurring on the Day of Vaccination and the following 7 Days after any Dose (Safety Analysis Set)
Table 14.3.2.3.1 Local Solicited Adverse Events and Maximum Grade Occurring on the Day of Vaccination and the following 7 Days after any Dose (Safety Analysis Set)
Table 14.3.2.4.1 Systemic Solicited Adverse Events and Maximum Grade Occurring on the Day of Vaccination and the following 7 Days after any Dose (Safety Analysis Set)
Table 14.3.2.6.1 Duration of Solicited Adverse Events Occurring on the Day of Vaccination and the following 7 Days after any Dose (Safety Analysis Set)

Table 14.3.2.16.1 Unsolicited Adverse Events by System Organ Class and Preferred Term Occurring on the Day of Vaccination and the following 28 Days after any Dose (Safety Analysis Set)
Table 14.3.2.16.2 Unsolicited Adverse Events by System Organ Class and Preferred Term Occurring on the Day of Vaccination and the following 28 Days after Dose 1 (Safety Analysis Set)
Table 14.3.2.16.3 Unsolicited Adverse Events by System Organ Class and Preferred Term Occurring on the Day of Vaccination and the following 28 Days after Dose 2 (Safety Analysis Set)
Table 14.3.2.17.1 Unsolicited Adverse Events for Duration of Trial by System Organ Class and Preferred Term (Safety Analysis Set)
Table 14.3.2.17.2 Related Unsolicited Adverse Events for Duration of Trial by System Organ Class and Preferred Term (Safety Analysis Set)
Table 14.3.2.20.1 Unsolicited Adverse Events by System Organ Class, Preferred Term, and Maximum Severity Occurring on the Day of Vaccination and the following 28 Days after any Dose (Safety Analysis Set)
Table 14.3.2.20.2 Unsolicited Adverse Events by System Organ Class, Preferred Term, and Maximum Severity Occurring on the Day of Vaccination and the following 28 Days after Dose 1 (Safety Analysis Set)
Table 14.3.2.20.3 Unsolicited Adverse Events by System Organ Class, Preferred Term, and Maximum Severity Occurring on the Day of Vaccination and the following 28 Days after Dose 2 (Safety Analysis Set)
Table 14.3.2.26.1 Adverse Events of Special Interest for Duration of Trial by System Organ Class and Preferred Term (Safety Analysis Set)
Table 14.3.2.29.1 Adverse Events Leading to Study Withdrawal by System Organ Class and Preferred Term (Safety Analysis Set)

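### SAP 10.5 has no dose 2 rule for partial AE start dates, so a day-missing AE that begins after dose 2 in the dose 2 month is usually dated before dose 2

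*SAP*

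**What the plan says.** For a partial start date in the vaccination year, SAP 10.5 states that "the start date month needs to be compared against the vaccination start date month, to determine the imputation rule to apply". Three branches matter here:

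- Later month, day missing: "If month is greater than the vaccination start date month and start date day is missing, the imputed start date is set to the beginning" (that is, the 1st).
- Same month ("If month is equal to the vaccination start date month and start date day is missing"): the vaccination day is used.
- Year only: "If month is missing, the imputed month and imputed day is the same as start of vaccination".

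Section 10.5 does not say which dose this vaccination start date refers to. Section 10.7.1 applies the imputed date to treatment emergence, where "an AE is defined as TEAEs if the start date/time is after the date/time of first vaccination", so dose 1 is the natural reading. Protocol 10.3.6 also uses one vaccination start date and has no rule for dose 2.

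The outputs, however, need a dose. SAP 12.7.1.1 says: "An overall summary of unsolicited AEs will be prepared for AEs occurring within 28 days after each dose, within 28 days after any dose". It also asks for the SOC/PT tables "separately for AEs occurring within the first 28 days after each vaccination". Appendix 4 keeps by-dose tables, for example 14.3.2.16.3, "Unsolicited Adverse Events by System Organ Class and Preferred Term Occurring on the Day of Vaccination and the following 28 Days after Dose 2".

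**The concern.** A rule that only has to settle whether an AE began after the first vaccination is being used to decide which dose an AE followed. In the dose 1 month it is cautious: an AE of unknown day goes to the vaccination day and stays on the post-dose side. In the dose 2 month it does the opposite and puts the AE before dose 2, unless dose 2 fell on the 1st.

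The primary safety objective (SAP 7.1) is the profile after one and after two doses, and the unsolicited AE endpoint is defined on each vaccination day and the following 28 days. At stake are the by-dose unsolicited AE tables 14.3.2.16.2/.3 and 14.3.2.20.2/.3. For an AE that truly followed dose 2, the error can only take it out of the dose 2 table. Where the imputed date falls in neither window, the AE also leaves the any-dose 28-day tables 14.3.2.16.1 and 14.3.2.20.1.

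**Working it through.** The plan gives no figure on this point, so there is none to reproduce.

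**Inputs**
- Dose 2 at dose 1 + 28 days, window -3/+14, so 25 to 42 days after dose 1 (SAP 6.2, Table 2).
- AE window for each dose: the dose date to dose date + 28 days (SAP 12.7.1.1, Appendix 4).
- Imputation as in SAP 10.5, with dose 1 as the reference.
- First-dose dates from 1 April to 1 July 2021, 92 dates with equal weight. This is an assumption; the documents give no enrolment dates.

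**Rule for a day-missing AE in the dose 2 month**
- If dose 2 falls in a later month than dose 1, the imputed date is the 1st of the dose 2 month.
- If both doses share a month, the imputed date is the dose 1 date.

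**Example 1.** Dose 1 on 20 May, dose 2 on 20 May + 28 days = 17 June, true onset 22 June with the day missing. The imputed date is 1 June, which is Day 13: inside the dose 1 window and 16 days before dose 2.

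**Example 2.** Dose 1 on 1 May, dose 2 on 1 May + 42 days = 12 June, true onset 20 June with the day missing. The imputed date is 1 June, 31 days after dose 1. Since 31 > 28 and 1 June precedes dose 2, the AE is in neither window.

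**Count over the 92 start dates**

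| Days from dose 1 to dose 2 | 1st of month: before dose 2, in dose 1 window | Doses share a month: set to dose 1 date | 1st of month: before dose 2, in neither window | Dose 2 on the 1st | Dated before dose 2 |
|---|---|---|---|---|---|
| 25 | 72 | 17 | 0 | 3 | 72 + 17 = 89 |
| 28 | 81 | 8 | 0 | 3 | 81 + 8 = 89 |
| 35 | 71 | 0 | 18 | 3 | 71 + 18 = 89 |
| 42 | 50 | 0 | 39 | 3 | 50 + 39 = 89 |

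So 89/92 = 97% of start dates at each interval. The three exceptions are the dates for which dose 2 falls on the 1st.

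**Start dates versus AEs.** The count describes where the rule puts a date; it does not say how often that is wrong. On average 51.6% of the days of the dose 2 month fall on or after dose 2. The other 48.4% precede it, and AEs that began then mostly do belong to dose 1.

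**Restricted to AEs that truly start on or after dose 2 within the dose 2 month** (all 365 first-dose dates of 2021, onset uniform over the dose 2 window; both are assumptions):
- Dose 2 on Day 29: 93.9% fall in the dose 1 window only and 6.1% in both.
- All days of the -3/+14 window weighted equally: 67.0% dose 1 only, 26.9% neither, 4.7% dose 2 only, 1.3% both.
- Dose 2 on Day 43: 30.1% dose 1, 63.8% neither, 6.1% dose 2.

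**If these AEs are set to the dose 2 date instead,** every one of them stays in the dose 2 window. With dose 2 on Day 29, that date is also dose 1 + 28 days. On the same assumptions, 54.0% of all day-missing AEs from the dose 2 window would then sit in both windows, so a tie rule is needed.

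**The case against.** The strongest reply is that this changes very little. Solicited AEs are recorded by diary day. Treatment emergence depends only on the first vaccination, and the whole-trial tables (14.3.2.17.1, 17.2 and 26.1) do not move. Unsolicited AEs are also entered in diaries for 28 days after each dose, with diary review at Days 29, 30, 43 and 57; missing data are queried (Protocol 11.4); and listings show the incomplete date as recorded. The analysis is descriptive, in 129 subjects, and the number of partial dates could be zero. All of this stands and limits the count. None of it corrects the rule: the check in 10.5 of start against resolution date can only move a start date earlier.

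The status of two of the tables is also unclear. SAP 12.7.1.1 marks the maximum-severity summary as outside the abbreviated scope, while Appendix 4 lists 14.3.2.20.1 to .3. Tables 14.3.2.16.2/.3 are not in doubt.

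A second reply is that anchoring to dose 2 has its own error, since some AEs that began earlier in that month would move to dose 2. That is true and should be stated with the rule. It is the same cautious choice that 10.5 already makes in the dose 1 month.

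Two stronger readings are tempting. One takes 81 of 92 (88%) at the 28-day interval, or 89 of 92, as the proportion of AEs misassigned. These are shares of calendar start dates, and about half the days of the dose 2 month precede dose 2. The other is that AEs always shift from dose 2 to dose 1. With a late dose 2 many fall in neither window, and at Day 43 that is the majority.

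**Conclusion.** The point holds as a small defect in a stated rule. Applied as written, SAP 10.5 dates a day-missing unsolicited AE in the dose 2 month before dose 2 unless dose 2 was given on the 1st: 89 of 92 start dates under the assumed April to July 2021 range. AEs that truly followed dose 2 are then counted under dose 1 or, with a late dose 2, in neither 28-day window.

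This rests on reading the vaccination start date as dose 1, which 10.5 does not define but 10.7.1 supports. The effect is confined to unsolicited AEs with a partial start date in the 28-day tables. The documents do not give their number, which is probably small, and they do not support a claim that the safety conclusions as a whole would change.

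**What to change.** Add two or three sentences to SAP 10.5:

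1. State that the vaccination start date means the first vaccination when treatment emergence is decided.
2. For the by-dose tables, if the AE month and year equal those of dose 2 and the day is missing, set the start to the dose 2 date unless the resolution date is before dose 2.
3. Count an AE imputed to the dose 2 date under dose 2 only. This settles the Day 29 overlap.

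Leave year-only dates under the existing rule. Without a month there is no ground for placing them at dose 2, and doing so would move dose 1 AEs wholesale.

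The cost is a few lines of text and of derivation code, with no new data. The downside is that some AEs that began earlier in the dose 2 month will be attributed to dose 2; a table footnote should say so.
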